9. Call schedules will also be used to determine specialist and midwives responsible for postpartum care of women during the intervention block. Midwives will be asked to hold an assigned emergency mobile phone to which alerts would be sent if abnormalities occur in the physiologic signs of enrolled women. This mobile phone will require password/pin access which will only be given to the enrolled clinicians. Specialists/consultants will also have the option to install a password protected mobile app to receive notifications and alerts and visualize data on their personal mobile phones as long as their phones meet minimum security and privacy measures (password protected and encrypted phone). Enrolled attending physicians with clinical responsibility during the intervention block will also be given the option to receive alerts to their personal mobile phones should abnormalities occur. Alerts will be sent to the emergency mobile phone and personal phones of enrolled specialists who mark themselves as on duty if any of abnormalities occur in physiologic signs as described in Table 1.

Alert messages will include the following text:

- Medical identification number and name (to allow the covering doctor to find and review relevant clinical information for the patient and fine the patient if needed.

Table 1: Predefined limits for clinician alerts

Physiologic sign	Cut off for alert
Heart rate (beats per minute), noted for >5 minutes	>120
Systolic Blood pressure (mmHg), any	>160 or <70
Diastolic blood pressure (mmHg), any	>110 or <30
Temperature (C) noted for >2 minutes	>40C
Respiratory Rate (breaths per min) noted for >5 minutes	>30

- Nature of abnormality e.g. Heart Rate = 140bpm, or Blood pressure= 180/110. Any clinical response to the abnormality will be left to the discretion of the covering doctor in accordance to current standard care guidelines at MRRH.

10. For clinical safety of the women participants, midwives receiving any alerts indicating the above vital sign abnormalities will be asked to inform one of the doctors on call. In the event of technical issues with the monitoring system, midwives will be able to access a research assistant who will be on 24 hours a day.

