**Descriptive statistics:**

Descriptive statistics will be analyzed according to the RE-AIM Framework as below.

**Reach:** Proportion of target population that participated in the intervention

- *Percent of women with successful placement of biosensor after delivery*
  - Determined by number of women with monitoring data from CH/ Number of women enrolled in Redcap
- *Time to initiation of monitoring*
  - Time from delivery date & time until start time of monitoring as recorded by RA in enrollment log
  - Time from delivery date & time until start time of vital sign data received by current health
  - Time from delivery date and time until start time of valid vital sign data from current health.
- *Total length of time of monitoring*
  - Length of time women wore the monitor, calculated from start/stop times recorded by RAs (mean  $\pm$  SD, median, IQR)
  - Length of time of vital sign data received by monitor, calculated from vital sign data received by CH (mean  $\pm$  SD, median, IQR)
  - Length of time of valid vital sign data received by monitor, calculated from vital sign data received by CH after excluding implausible values.
- *Percent of women participating in monitoring for 24 hours*
  - Number of women wearing the monitor for  $\geq 24$  hours / Number of women enrolled
  - Number of women with vital sign data received by monitor for  $\geq 24$  hour/Number of women enrolled.

**Efficacy:** Success rate if implemented as in guidelines

- *Percent of women with HR, BP, RR and Tp available at least every 4 hours for 24 hours after delivery*
  - *Intent to treat:*
    - Number of women with HR (RR, Tp) measured every 4 hours for 24 hours/ Number of eligible women in block
    - Number of women with BP measured every 6 hours for 24 hours/Number of eligible women in block
  - *Actual allocation*
    - Number of women with HR (RR, Tp) measured every 4 hours for 24 hours/ Number of women with CH output
    - Number of women with BP measured every 6 hours for 24 hours/ Number of women with CH monitoring

**Commented [BAA6]:** Restrict to women in block vs women eligible

NCT ID: 2019P000885

Document Date: September 26th 2021

- *Percent of appropriate alerts sent (restricted to those with CH output)*
  - Number of women with alerts sent for HR (RR, Tp, BP)/ number of women with CH monitoring
  - Number of women with “appropriate” alerts sent for HR (RR, Tp, BP)/ number of

Predefined limits for clinician alerts	

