Physiologic sign	Cut off for alert
Heart rate (beats per minute),	Mean >120 beats per minute for 10 minutes
Systolic blood pressure (mmHg), any	>160 or <70
Diastolic blood pressure (mmHg), any	>110 or <30
Temperature (C)	Mean ≥ 38C for 10 minutes
Respiratory rate (breaths per min)	Mean ≥ 30 breaths per minute for 10 minutes

women with CH monitoring. (Appropriate defined as meeting the thresholds established by study protocol as in below)

- *Percent of alert receipt*
  - Number of alerts noted as received/Number of alerts sent. (Alerts received retrieved from midwife survey data on redcap using date/shift to collate; alerts sent from CH collated by date/shift.

**Adoption:** Proportion of practitioners adopting this intervention

- *Percent of eligible clinicians participating in wireless monitoring*
  - Midwives
    - Number of eligible midwives consenting/Number of eligible midwives
    - Number of midwives receiving phone/Number of eligible midwives scheduled
    - Number of midwives logging into system per shift/ Number of eligible midwives per shift (**Requires access to CH backend data on user logins and signing into on duty**)
- *Number of clinical actions in response to alerts – based on data from redcap surveys.*
  - Midwives
    - Time to review of alert
      - Proportion of alerts received reviewed <5 minutes, <15 mins, < 30 mins, 1 hr or ≥)
    - Proportion of patients assessed after report of an alarm (using end of shift survey data)
    - Proportion of patients with a clinical exam/procedure after report of receipt of an alarm (using end of shift survey data)
    - Proportion of patients with escalation in notification after report of receipt of an alarm (i.e., notification of someone else)

RE-AIM Implementation Science Framework			
Metric	Dimension	Study Measure	Data source
Implementation	Extent to which the intervention is	• Fidelity of implementation to the study protocol	• Documentation of any necessary adjustment to

NCT ID: 2019P000885

Document Date: September 26th 2021

	implemented in the real world		the protocol after study enrollment begins • Documentation of disruptions due to external factors
Maintenance	Sustainability of program over time	• Sustainability of reach, efficacy and adoption as measured by stability of measures over study period	• Above sources reviewed over the 12-month study period

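### Three of the SAP's five alert limits differ from the protocol limits it says it applies, and its Reach percentages divide by women enrolled instead of the target population

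*SAP*

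**What the plan says.** **Alert limits.** Protocol, Study Procedures item 9, sends alerts when signs pass the limits in its Table 1. Three rows carry a duration: "Heart rate (beats per minute), noted for >5 minutes" with a cut-off above 120, "Respiratory Rate (breaths per min) noted for >5 minutes" with a cut-off above 30, and "Temperature (C) noted for >2 minutes" with a cut-off above 40C. The two blood pressure rows apply to any reading.

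The SAP (Aim 2, Efficacy) ties an appropriate alert to the protocol: "Appropriate defined as meeting the thresholds established by study protocol as in below". Its own table gives "Mean >120 beats per minute for 10 minutes", "Mean ≥ 30 breaths per minute for 10 minutes" and "Mean ≥ 38C for 10 minutes", with the same two blood pressure rows as the protocol.

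**Unit of the alert measure.** The protocol's RE-AIM table and the SAP both title this measure as a percentage of alerts. The SAP's formulas count women. The first is "Number of women with alerts sent for HR (RR, Tp, BP)/ number of women with CH monitoring"; the second puts women with appropriate alerts over the same denominator.

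**Reach.** Both documents define Reach as the share of the target population taking part. The SAP then gives three Reach percentages: sensor placement, 24 hours of wear, and 24 hours of data received. All three are divided by women enrolled. Under Analysis Cohorts and Datasets, enrolled women are those who were screened, found eligible and given a study number.

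**The concern.** The SAP's sentence and the table beneath it cannot both be followed. If the device ran the protocol limits, the table scores alerts against a rule that never operated. If it ran the SAP limits, the scoring is right, but the attribution to the protocol (or the protocol table itself) is wrong. A reader of the results could not tell which rule the word *appropriate* refers to.

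For Reach, the purpose of the measure is to show how much of the target population the intervention got to. A denominator limited to enrolled women removes those it did not reach: women who declined, were missed at screening, or were screened and not enrolled. Aim 2 is a stated aim of a type 2 hybrid trial, so these percentages will be read as results.

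**Working it through.** **1. The two alert tables side by side**

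| Sign | Protocol Table 1 | SAP Aim 2 table | Same? |
|---|---|---|---|
| Heart rate | >120 for >5 min | mean >120 over 10 min | No |
| Respiratory rate | >30 for >5 min | mean ≥30 over 10 min | No |
| Temperature | >40C for >2 min | mean ≥38C over 10 min | No |
| Systolic BP | >160 or <70, any | >160 or <70 | Yes |
| Diastolic BP | >110 or <30, any | >110 or <30 | Yes |

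The disagreement runs both ways, reading the protocol durations as sustained values:
- A steady 39C for 10 minutes meets the SAP rule but not the protocol rule.
- A steady respiratory rate of 30 for 10 minutes meets the SAP rule (≥30) but not the protocol rule (>30).
- A heart rate of 125 for 6 minutes with 100 in the surrounding minutes meets the protocol rule. The 10-minute mean is (6 × 125 + 4 × 100)/10 = 115, so it fails the SAP rule.
- A heart rate of 150 for 4 minutes and 105 for 6 has mean (4 × 150 + 6 × 105)/10 = 123. It meets the SAP rule, but only 4 minutes are above 120, so it fails the protocol rule.

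The frequency of such cases depends on the vital-sign data and cannot be derived from the documents.

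**2. Women or alerts (illustrative numbers)**

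Take 100 monitored women, of whom 20 have alerts, and count a woman if she has at least one appropriate alert.
- If every alert is appropriate, the SAP formula gives 20/100 = 20%, and the alert-level share is 100%.
- If each of the 20 women has 1 appropriate alert and 4 others, the SAP formula again gives 20/100 = 20%. The alert-level share is 20/(20 × 5) = 20%.

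The SAP figure is the same in both cases. It mainly reflects how many women had an abnormal sign.

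**3. Reach**

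Inputs from Protocol, Sample Size: about 112 emergency cesareans per two-week block, 85% consent, 95 women per block, 13 intervention blocks.

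The plan's own figure reproduces: 112 × 0.85 = 95.2, taken as 95; 13 × 95 = 1,235.

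Target population, treating all emergency cesareans as eligible as the sample size section does: 13 × 112 = 1,456.

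If every enrolled woman is monitored:
- SAP formula: 1,235/1,235 = 100%.
- Target-population Reach: 1,235/1,456 = 84.8%.
- Ratio: 1,456/1,235 = 1.18.

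The ratio does not depend on the placement rate, which cancels. With 90% of enrolled women monitored (assumed), the SAP formula gives 90% and the target-population figure is 0.90 × 0.85 = 76.5%.

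The ratio does depend on consent, since it is 1 divided by the consent share. Over an assumed range it is 1/0.90 = 1.11, 1/0.80 = 1.25 and 1/0.70 = 1.43.

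**The case against.** **The SAP limits may be the ones in use.** The SAP prints exact numbers that an analyst would simply apply. The protocol's risk section allows adjustment for alert fatigue, and the Implementation row of the RE-AIM framework plans to document such changes. This stands as far as it goes. A reader might infer that alerts will be mis-scored, and the documents do not support that, because they do not show the device settings. But neither document records a change of limits or its date, and the SAP still credits its limits to the protocol.

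**Decliners may not be part of the target population.** The protocol lists willingness to wear the sensor as an inclusion criterion, and the 1.18 consists entirely of decliners. That makes the definition of *eligible* a choice to be stated. The SAP has already made it for Aim 1, where women who declined consent or were missed count as eligible in the intervention periods. A measure of participation that excludes everyone who declined would say little.

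**The eligible count is available elsewhere.** This is correct. The intent-to-treat Efficacy measures already divide by eligible women in the block, and the Aim 1 event rates use all eligible women. A reader might infer that a fall in consent would go unseen in Maintenance. It would not: with other things equal, a fall from 90% to 70% (assumed) would lower intent-to-treat Efficacy by a factor of 0.70/0.90 = 0.78. Only the Reach lines would fail to move.

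**Controls in the denominator.** The enrolled cohort formally includes control-block women, so a reader might infer that Reach could come out near 1,235/2,470 = 50%. That reading is strained. Controls have record review only, and the SAP ties eligibility for monitoring to an allocated monitoring block.

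**Smaller points.** The SAP does not say how to class a woman with both kinds of alert, although at least one appropriate alert is the natural reading. It also scores blood pressure 6-hourly under a 4-hourly heading, although the formula itself is explicit. The first is missing detail and the second editorial.

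**Conclusion.** Two contradictions stand on the documents' own words.

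First, three of the five SAP alert limits are not those of the protocol to which the SAP attributes them. Whether this is an outdated table or attribution, or a real scoring error, cannot be settled from the documents. No size can be put on it. The woman-level formula also does not deliver the percentage of alerts named in its title.

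Second, the SAP's Reach formulas as written report a different quantity from the one defined. The overstatement is about 1.18 times (100% against 84.8% with all enrolled women monitored). That rests on the protocol's planned 112 and 95 women per block, on all emergency cesareans being eligible, and on counting decliners as eligible as Aim 1 does.

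Both points concern descriptive Aim 2 measures without a test. The Aim 1 comparison is unaffected. The changes should be made, but the trial's main conclusion does not hang on them.

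**What to change.** **Alerts.** Confirm from the device settings record which limits ran and between which dates. Make the protocol and SAP tables agree, and score each alert against the limits in force on its date. Nothing here says which limits are clinically right. Keep the woman-level rates and add appropriate alerts divided by all alerts sent. Label the new percentage as a check that the device followed its rules, since it does not measure clinically false alerts.

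**Reach.** Divide the placement and 24-hour percentages by all eligible women in intervention blocks, with eligibility as in the Aim 1 intention-to-treat rule, regardless of consent. Keep the percentage among enrolled intervention-block women as a separate, labelled measure.

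**Cost.** SAP wording, a check of the settings record, and a protocol table correction if that table is out of date. The eligible count is already needed for intent-to-treat Efficacy and Aim 1, and device alarm data are already a listed source, so no new participant data are required.
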